14.5. Vital Signs

Blood Pressures and Heart Rate baselines are defined as the mean of values obtained from the last 2 weeks of screening including Day 1 prior to the first dose.

Descriptive statistics for vital signs and their changes from baseline at each visit and at the end of study will be presented.

Vital sign values are potentially clinically significant (PCS) if they meet both the observed value criteria and the change from baseline criteria listed in [Table 6](#) below. The number and percentage of patients with post-baseline PCS values will be tabulated by dose level cohort (for open-label component) /treatment group (for double-blind component). The percentages are to be calculated relative to the number of patients with baseline and at least one post-baseline assessment. The numerator is the total number of patients with at least one post-baseline PCS vital sign value. Shift tables may be presented.

Patient incidence for each abnormality will be calculated based on patients with a baseline value and at least one post-baseline value for criteria requiring baseline or patients with at least one post-baseline value for criteria not requiring baseline. If differential dropout is observed between the two treatment arms, then the exposure adjusted incidence rate EAIR (per 100 patient years at risk) will be calculated regarding each abnormality.

Line plots of mean and mean change from baseline of vital sign parameters over time with the associated standard error will be provided.

A supportive listing of patients with post-baseline PCS values will be provided including the patient ID, study center, baseline, and post-baseline values. Values from unscheduled time points will not be used in post-baseline analysis, but will be listed.

Table 6: Criteria for Potentially Clinically Significant Vital Signs

Vital Sign Parameter	Flag	Criteria*	
		Observed Value	Change from Baseline
Systolic Blood Pressure (mmHg)	High	≥ 170	Increase of ≥ 20
	Low	≤ 90	Decrease of ≥ 20
Diastolic Blood Pressure (mmHg)	High	≥ 110	Increase of ≥ 15
	Low	≤ 45	Decrease of ≥ 15
Pulse Rate (bpm)	High	≥ 120	Increase of ≥ 20
	Low	≤ 50	Decrease of ≥ 20
Weight (kg)	High	-	Increase of $\geq 10\%$
	Low	-	Decrease of $\geq 10\%$

*Except for body weight, a post-baseline value is considered as a PCS value if it meets both criteria for observed value and change from baseline.

14.6. Electrocardiogram (ECG)

ECG findings are summarized in shift tables that include cross-tabulation of 'Normal', 'Abnormal NCS', and 'Abnormal CS'. Baseline value is the last non-missing measurement on or prior to the first dose. Patients with a baseline value and at least one post-baseline value will be included in the summary.

ECG data are presented in the data listing.

14.7. ECOG Performance Status

For ECOG performance status, the shift from baseline to the worst and best during the treatment will be displayed in cross tabulations. Baseline value is the last non-missing measurement on or prior to the first dose. Patients with a baseline value and at least one post-baseline value will be included in the summary.

14.8. Pregnancy Test

Findings from the pregnancy test will only be listed if applicable.

15. DATA SAFETY MONITORING BOARD

Safety data and dosing decisions will be monitored on an ongoing basis. In addition, ongoing review of safety data will be completed by an independent Data Safety Monitoring Board (DSMB) on a pre-defined periodic basis. The role and function of the DSMB will be defined in a DSMB charter.

16. INTERIM ANALYSIS

A preliminary analysis of the open-label component was conducted at the end of the open-label component of the study. In the double-blind component, the primary efficacy analysis will be conducted when all randomized patients have completed 28 weeks of treatment or early discontinued. A table of content (ToC) lists a subset of tables, figures, and listings for the Week 28 primary analysis in [Appendix 19.9](#). All other planned analyses outlined in this SAP will not be conducted until the end of study. The Week 28 analysis will be conducted by a small unblinded group not directly involved in the day-to-day study conduct. The study team will remain blinded until the final database lock and study unblinding. A detailed Data Access Plan summarizes the maintenance of blinding for the rest of the study.

No other formal interim analysis is planned.

17. CHANGES FROM THE PROTOCOL-SPECIFIED ANALYSES

3. Exploratory analyses on time to transfusion independence and time to 50% reduction in pRBC transfusion are added in this SAP due to clinical interest, although they are not in the protocol.
4. The 52 weeks analysis on the primary endpoint is regarded as a secondary endpoint and been included in the sequential gatekeeping procedure.
5. Based on results from prior roxadustat studies, measuring HRQoL 2-4 weeks after Hb “peaks” or stabilizes is shown to be most informative. In order to capture the treatment effect on Physical Function/fatigue before it wears off, Week 9 will be used as the primary time-point for HRQoL hypothesis testing in the sequential gatekeeping procedure.
6. Based on the re-estimated sample size of 120, 140 patients were enrolled in the double-blind component of the study.

19. APPENDIX

19.1. Dose Adjustment Rules for Patients who have TI for ≥ 56 Days

A modified dose adjustment algorithm will apply to patients who have attained TI ≥ 56 days (Maintenance Phase). The down titration of the dose is allowed at any time.

Change in Hb over past 4 weeks (g/dL)	Hemoglobin Values (g/dL)			
	<10.5	10.5 to 12.9	>13.0	≥ 13.5
< -1.0 (or had RBC transfusion within 4 weeks)	↑	↑	No change	Hold, then resume dosing when: Hb <12 g/dL, at a dose that is reduced by one dose steps Patients are to return weekly to monitor Hb until dosing can be resumed
-1.0 to 1.0	↑	No change	↓	
>1.0	No change	↓	↓	

Dose Adjustment for Excessive Hematopoiesis:

At any time during the Treatment Period if Hb increases by > 2.0 g/dL within 4 weeks, the dose should be reduced by one dose step.

19.2. Pharmacokinetics / Pharmacodynamics Analyses

Blood samples will be collected at the study site for determination of roxadustat plasma concentrations and erythropoietin levels at 1-3 and 3-5 hours after dosing at clinic on Day 1 (Week 1) as well as 4-6 hours at Week 5 and 8-10 hours at Week 21 after self-administration at home or at the clinic.

Population PK/PD Analysis will be done outside of the SAP, which will focus on safety and efficacy.

19.3. Data Handling Conventions

19.3.1. Analysis Windows

Tables below present the visits assigned for efficacy and safety analyses corresponding to the range of treatment days (window) during which an actual visit may have occurred.

The analysis windows will be only applied to those assessments up to the day before the first week of follow-up visit. Assessments obtained afterwards are considered follow-up assessments. For follow-up assessments, only follow-up assessments on scheduled follow-up visits (i.e. nominal follow-up visits) will be summarized unless otherwise specified.

If more than one assessment is available in the same window, the last assessment is used for analysis. Assessments that do not fall in any windows will not be included in analyses unless otherwise specified. However, all post-baseline assessments will be used for PCS value determination and all assessments will be presented in the data listings.

Table 7.1 Analysis Visit Windows (General)

Analysis Visit	Visit Scheduled Day ^a	Window
Baseline	Day 1	Up to Day 1 Pre-Dose
Week 3	Day 7*(Week # -1)+1	[Day 1 Post-Dose, Scheduled Day +7)
Weeks 5, 7, 9, 11...27	Day 7*(Week # -1)+1	[Scheduled Day -7, Scheduled Day +7)
Week 28 ^b	Day 7*(Week #)+1	[Scheduled Day -7, Scheduled Day +7)
Weeks 31	Day 7*(Week # -1)+1	[Scheduled Day -7, Scheduled Day +14)
Week 35, 39, 43	Day 7*(Week # -1)+1	[Scheduled Day -14, Scheduled Day +14)
Week 47	Day 7*(Week # -1)+1	[Scheduled Day -14, Scheduled Day +21)
Week 52 ^c	Day 7*(Week #)+1	[Scheduled Day -21, Up to Week 4 Follow up)

^a: Relative to the first study medication date. For example, Day 1 = the first dose date of study medication.

^b: Week 28 visit should be conducted at the end of 28 weeks of treatment (2 weeks after Week 27 Visit).

^c: Week 52 Visit should be scheduled at the end of 52 weeks treatment (6 weeks after Week 47 visit).

Table 7.2 Analysis Visit Windows for Lipid Parameters

Derived Visit	Visit Scheduled Day ^a	Window
Baseline	Day 1(first dose day)	Up to Day 1 Pre-Dose
Week 5	Day 7 * (Week # -1) +1	[Day 1 Post-dose, Scheduled Day + 56)
Week 21	Day 7 * (Week # -1) +1	[Scheduled Day - 56, Scheduled Day + 28)
Week 28 ^b	Day 7 * (Week #) +1	[Scheduled Day - 28, Scheduled Day + 35)
Week 39	Day 7 * (Week # -1) +1	[Scheduled Day - 35, Scheduled Day + 49)
Week 52 ^c	Day 7 * (Week #) +1	[Scheduled Day -49, Up to Week 4 follow-up)

^a: Relative to the first study medication date. For example, Day 1 = the first dose date of study medication.

^b: Week 28 visit should be conducted at the end of 28 weeks of treatment (2 weeks after Week 27 Visit).

^c: Week 52 Visit should be scheduled at the end of 52 weeks treatment (6 weeks after Week 47 visit).

Table 7.3 Analysis Visit Windows for Serum Iron, Ferritin, TIBC, UIBC, TSAT, Transferrin, Vital Sign, Serum Chemistry

Derived Visit	Visit Scheduled Day ^a	Window
Baseline	Day 1 (first dose day)	Up to Day 1 Pre-Dose
Week 5	Day 7 * (Week # -1) +1	[Day 1 post-dose, Scheduled Day + 14)
Weeks 9, 13, 17, 21	Day 7 * (Week # -1) +1	[Scheduled Day - 14, Scheduled Day + 14)
Week 25	Day 7 * (Week # -1) +1	[Scheduled Day - 14, Scheduled Day + 14)
Week 28 ^b	Day 7 * (Week #) +1	[Scheduled Day - 14, Scheduled Day + 35)
Week 39	Day 7 * (Week # -1) +1	[Scheduled Day - 35, Scheduled Day + 49)
Week 52 ^c	Day 7 * (Week #) +1	[Scheduled Day - 49, Up to Week 4 follow-up)

^a: Relative to the first study medication date. For example, Day 1 = the first dose date of study medication.

^b: Week 28 visit should be conducted at the end of 28 weeks of treatment (2 weeks after Week 27 Visit).

^c: Week 52 Visit should be scheduled at the end of 52 weeks treatment (6 weeks after Week 47 visit).

Table 7.4 Analysis Visit Windows for Hepcidin

Derived Visit	Visit Scheduled Day ^a	Window
Baseline	Day 1 (first dose day)	Up to Day 1 Pre-Dose
Week 5	Day 7 * (Week # -1) +1	[Day 1 post-dose, Scheduled Day + 28)
Week 13	Day 7 * (Week # -1) +1	[Scheduled Day - 28, Scheduled Day + 28)
Week 21	Day 7 * (Week # -1) +1	[Scheduled Day - 28, Scheduled Day + 14)
Week 25	Day 7 * (Week # -1) +1	[Scheduled Day - 14, Scheduled Day + 14)
Week 28 ^b	Day 7 * (Week #) +1	[Scheduled Day - 14, Scheduled Day + 35)
Week 39	Day 7 * (Week # -1) +1	[Scheduled Day - 35, Scheduled Day + 49)
Week 52 ^c	Day 7 * (Week #) +1	[Scheduled Day - 49, Up to Week 4 follow-up)

^a: Relative to the first study medication date. For example, Day 1 = the first dose date of study medication.

^b: Week 28 visit should be conducted at the end of 28 weeks of treatment (2 weeks after Week 27 Visit).

^c: Week 52 Visit should be scheduled at the end of 52 weeks treatment (6 weeks after Week 47 visit).

Table 7.5 Analysis Visit Windows for ECG

Derived Visit	Visit Scheduled Day ^a	Window
Baseline	Day 1 (first dose day)	Up to Day 1 Pre-Dose
Week 28 ^b	Day 7 * (Week #) +1	[Day 1 post-dose, Scheduled Day + 84)
Week 52 ^c	Day 7 * (Week #) +1	[Scheduled Day - 84, Up to Week 4 follow-up)

^a: Relative to the first study medication date. For example, Day 1 = the first dose date of study medication.

^b: Week 28 visit should be conducted at the end of 28 weeks of treatment (2 weeks after Week 27 Visit).

^c: Week 52 Visit should be scheduled at the end of 52 weeks treatment (6 weeks after Week 47 visit).

**Table 7.6 Analysis Visit Windows for CBC
(Only in Subjects Enrolled before Effective Day of Protocol Amendment 3)**

Analysis Visit	Visit Scheduled Day ^a	Window
Baseline	Day 1	Up to Day 1 Pre-Dose
Week 2	Day 7*(Week # -1)+1	[Day 1 Post-Dose, Scheduled Day +3]
Week 3,4	Day 7*(Week # -1)+1	[Scheduled Day -3, Scheduled Day +3]
Week 5	Day 7*(Week # -1)+1	[Scheduled Day -3, Scheduled Day +7]
Weeks 7, 9, 11...27	Day 7*(Week # -1)+1	[Scheduled Day -7, Scheduled Day +7]
Week 28 ^b	Day 7*(Week #)+1	[Scheduled Day -7, Scheduled Day +7]
Weeks 31	Day 7*(Week # -1)+1	[Scheduled Day -7, Scheduled Day +14]
Week 35, 39, 43	Day 7*(Week # -1)+1	[Scheduled Day -14, Scheduled Day +14]
Week 47	Day 7*(Week # -1)+1	[Scheduled Day -14, Scheduled Day +21]
Week 52 ^c	Day 7*(Week #)+1	[Scheduled Day -21, Up to Week 4 Follow up)

^a: Relative to the first study medication date. For example, Day 1 = the first dose date of study medication.

^b: Week 28 visit should be conducted at the end of 28 weeks of treatment (2 weeks after Week 27 Visit).

^c: Week 52 Visit should be scheduled at the end of 52 weeks treatment (6 weeks after Week 47 visit).

Table 7.7 Analysis Visit Windows for EQ-5D-5L, PROMIS Physical Function and PROMIS Fatigue Function

Derived Visit	Visit Scheduled Day ^a	Window
Baseline	Day 1(first dose day)	Up to Day 1 Pre-Dose
Week 9	Day 7 * (Week # -1) +1	[Day 1 post-dose, Scheduled Day + 28)
Weeks 17	Day 7 * (Week # -1) +1	[Scheduled Day - 28, Scheduled Day + 42)
Week 28 ^b	Day 7 * (Week #) +1	[Scheduled Day - 42, Scheduled Day + 84)
Week 52 ^c	Day 7 * (Week #) +1	[Scheduled Day - 84, Up to Week 4 follow-up)

^a: Relative to the first study medication date. For example, Day 1 = the first dose date of study medication.

^b: Week 28 visit should be conducted at the end of 28 weeks of treatment (2 weeks after Week 27 Visit).

^c: Week 52 Visit should be scheduled at the end of 52 weeks treatment (6 weeks after Week 47 visit).

Table 7.8 Analysis Visit Windows for ECOG

Derived Visit	Visit Scheduled Day ^a	Window
Baseline	Day 1(first dose day)	Up to Day 1 Pre-Dose
Week 5	Day 7 * (Week # -1) +1	[Day 1 post-dose, Scheduled Day + 28)
Week 13	Day 7 * (Week # -1) +1	[Scheduled Day - 28, Scheduled Day + 14)
Weeks 17	Day 7 * (Week # -1) +1	[Scheduled Day - 14, Scheduled Day + 28)
Weeks 25	Day 7 * (Week # -1) +1	[Scheduled Day - 28, Scheduled Day + 14)
Week 28 ^b	Day 7 * (Week #) +1	[Scheduled Day - 14, Scheduled Day + 84)
Week 52 ^c	Day 7 * (Week #) +1	[Scheduled Day - 84, Up to Week 4 follow-up)

^a: Relative to the first study medication date. For example, Day 1 = the first dose date of study medication.

- ^b: Week 28 visit should be conducted at the end of 28 weeks of treatment (2 weeks after Week 27 Visit).
^c: Week 52 Visit should be scheduled at the end of 52 weeks treatment (6 weeks after Week 47 visit).

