#### 6.4 Follow-up Period after EOT or Early Termination of study medication

Patients who discontinue study medication early (before week 52) will have an EOT visit and then a 4 week follow-up visit. They will then be followed up at a reduced visit schedule of every 8 weeks until the end of the study (see [Table 2](#)).

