12.3.3.7. Mean Change from Baseline in Fatigue Subscale of PROMIS

Fatigue will be measured in the study using the 13-item fatigue scale of the FACIT Measurement System, each item is scored on a 5-point rating scale ranging from 1 to 5 depicting “not at all” to “very much”, with higher scores indicating better functioning. The questionnaire is designed for self-completion by patients and will be administered at baseline, Week 9, Week 17, Week 28 and Week 52(or EOT).

PROMIS items are not scored as sums, but rather on a standardized T-score metric ([Appendix 19.6](#)) using IRT. The standardized norm-based T-scores will be used in the summary. The mean change from Baseline in the PROMIS-SF v1.0 Fatigue 13a score over time will be summarized and analyzed using the FAS and PPS Population. The analysis window is defined in [Appendix 19.3.1](#).

A mixed model for repeated measures (MMRM) with treatment, visit, treatment*visit, and stratification factors as fixed effects, the baseline score value and baseline*visit interaction as covariate will be used to assess treatment difference. The LSM and the corresponding 95% confidence intervals for the differences between roxadustat and the placebo group (roxadustat – placebo) will be presented along with the p-values for the treatment differences resulting from the model. The LSM for the difference will be considered clinically meaningful if it exceeds the distribution-based minimal clinically important difference (MCID) and will be marked in the results, see [Section 19.8.1](#) for details of MCID. An unstructured variance-covariance structure will be used to model the within-patient errors. This variance-covariance matrix will be estimated across treatment groups. If the model fails to converge, then the covariance structure that converges and with the highest REML log likelihood will be used.

Missing value will be handled by the MMRM model, utilizing data from all visits and all patients.

A sensitivity analysis will be conducted using Analysis of Covariance (ANCOVA) model with Last Observation Carries Forward (LOCF) imputation, see [Section 19.8.2](#) for details.

Week 9 and week 52 are the analysis endpoint for 28-week and 52-week analysis respectively, the p-value obtained will be reported.

This analysis will take into account the potential intercurrent events as follows:

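### Keeping the last assessment in each visit window lets an early end-of-treatment questionnaire replace a completed Week 9 score in gatekept Tests 8 to 10

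*SAP*

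**What the plan says.** SAP 19.3.1 sets the scope of the windows: "The analysis windows will be only applied to those assessments up to the day before the first week of follow-up visit". The EOT visit comes before the 4-week follow-up visit, so EOT values are windowed by treatment day like any other. When a window holds several values, "If more than one assessment is available in the same window, the last assessment is used for analysis". No preference is given to the nominal visit or to the value nearest the scheduled day.

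Table 7.7 covers EQ-5D-5L, PROMIS Physical Function and PROMIS Fatigue. Its Week 9 window is "Day 1 post-dose, Scheduled Day + 28" and its Week 28 window is "Scheduled Day - 42, Scheduled Day + 84", each with an exclusive upper bound.

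Early stoppers do have an EOT visit. Protocol 6.4 says: "Patients who discontinue study medication early (before week 52) will have an EOT visit and then a 4 week follow-up visit". Protocol Appendix B marks HRQoL, ECOG, lipids, iron, chemistry and hepcidin at that visit. SAP 12.3.3.7 gives the fatigue schedule as "administered at baseline, Week 9, Week 17, Week 28 and Week 52(or EOT", and 12.3.3.6 and 12.3.3.8 give the same time points.

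SAP 12.3.2 (Table 4) defines Tests 8 to 10 as change from baseline at Week 9. SAP 17, item 5, explains the choice: "In order to capture the treatment effect on Physical Function/fatigue before it wears off, Week 9 will be used as the primary time-point".

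**The concern.** Tests 8 to 10 target the score at Week 9. Where a patient has such a score, taken on schedule and while on treatment, nothing that happens later should remove it. The last-in-window rule removes it if the patient stops soon afterwards and completes an EOT form inside the same wide window.

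Protocol 6.5 allows only 2 days either side for visits from Week 7 on. A second questionnaire after about Day 59 in the Week 9 window will therefore usually be an EOT form, so in practice the replacement falls on patients who discontinue. If stopping rates or reasons differ between arms, so does the replacement. The value used is then not the one SAP 17 chose Week 9 to capture.

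Nothing else in the SAP repairs this:

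- The worst-score substitution after an adverse-event discontinuation (12.3.3.6 to 12.3.3.8) applies only to missing scores, and here none is missing.
- The per-protocol set (5.3.3) requires at least 8 weeks of treatment, which a patient stopping on Day 58 or later has received.
- The LOCF analysis (19.8.2) does not change the window rule.

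**Working it through.** **Inputs.** Scheduled days and windows come from SAP Tables 7.2 to 7.8, the EOT assessments from Protocol Appendix B, and the double-blind N of 140 from SAP 17, item 6. The protocol text supplied is Amendment 02, while the SAP cites Amendment 03. The SAP's own HRQoL schedule also includes EOT.

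**Reproducing the SAP's days.** Week 27 is 7 × 26 + 1 = Day 183. The footnote reads "Week 28 visit should be conducted at the end of 28 weeks of treatment (2 weeks after Week 27 Visit", and 183 + 14 = 197 = 7 × 28 + 1, so Week 28 is Day 197. Week 9 is 7 × 8 + 1 = Day 57, Week 17 is Day 113 and Week 52 is 7 × 52 + 1 = Day 365.

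**Do the Table 7.7 windows join?**

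- 57 + 28 = 85 = 113 − 28
- 113 + 42 = 155 = 197 − 42
- 197 + 84 = 281 = 365 − 84

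They join without gap or overlap, which confirms that upper bounds are exclusive. Week 9 is Day 1 post-dose to Day 84, and Week 28 is Days 155 to 280.

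**Largest lag of a replacing EOT value, counted from the scheduled day.**

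| Window | Scheduled day | Last day in window | Largest lag |
|---|---|---|---|
| HRQoL Week 9 | 57 | 84 | 27 days |
| HRQoL and ECOG Week 28 | 197 | 280 | 83 days |
| Hepcidin, iron, chemistry, lipids Week 28 | 197 | 231 | 34 days |

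For example, a patient completes Week 9 on Day 57, stops on Day 78 and fills in the EOT form on Day 80. Both forms fall in Days 1 to 84, the Day 80 form is the later, and it becomes the Week 9 value.

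**How many patients.** The documents give no discontinuation rate, so this part rests on assumption. Let c be the fraction completing 52 weeks (364 days), with constant hazard h = −ln(c)/364 and S(d) = exp(−h·d).

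| | c = 0.8 | c = 0.5 |
|---|---|---|
| h per day | 0.000613 | 0.001904 |
| Stop on Days 58-84: S(57) − S(84) | 0.966 − 0.950 = 0.016 | 0.897 − 0.852 = 0.045 |
| Of 140 | 2.2 | 6.3 |
| Stop on Days 198-280: S(197) − S(280) | 0.886 − 0.842 = 0.044 | 0.687 − 0.587 = 0.100 |
| Of 140 | 6.2 | 14.1 |

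A different assumption, 10-40% stopping by Day 197, gives about 2-8 patients at Week 9 and 5-16 at Week 28. All these counts treat every stop as producing an EOT form on the stop date, after a completed scheduled form. They are therefore upper figures for each assumed rate.

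**How large a shift.** For illustration, assume an 84:56 split (3:2 of 140), a T-score SD of 10, EOT scores 5 points worse than the Week 9 scores they replace, and replacement in 1.6% of one arm and 4.5% of the other. The treatment difference moves by 0.029 × 5 = 0.15 points. The standard error is 10 × √(1/84 + 1/56) = 1.73, so the shift is under 0.1 standard errors. At 10 points worse it is 0.29 points, under 0.2 standard errors.

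**The case against.** The rule is pre-specified, deterministic and identical in both arms, and the calculation above shows only a small effect on three tests that come last in a sequence of ten. That is a fair account of the size. It does not explain why an observed on-schedule score should be dropped because of a later event.

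The SAP's listing of the last time point as Week 52 or EOT might mean that every EOT form is filed as Week 52. However, 19.3.1 assigns by treatment day and Table 7.7 starts Week 52 at Day 281, so the written rule puts an EOT form from Days 58-84 into Week 9. If filing as Week 52 was intended, the SAP needs to say so.

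Three stronger readings are tempting, and the documents do not support them:

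- *Week 28 replacements also corrupt the gatekept tests.* Tests 8 to 10 are at Week 9, and 12.3.3.6 to 12.3.3.8 name only Week 9 and Week 52 as HRQoL analysis endpoints. A replaced Week 28 score reaches those tests only indirectly, through the shared repeated-measures model.
- *Every patient stopping in the window loses the Week 9 score.* Protocol 4.3 lists death, loss to follow-up and withdrawal of consent among the reasons for stopping, so some will have no EOT form. Others who stop near Day 84 will have an EOT visit that falls in the Week 17 window.
- *The replacing score is always taken at failure or an adverse event, so the bias has a known sign.* Reasons for stopping also include patient decision and site closure. The direction cannot be determined from the documents.

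**Conclusion.** The concern holds for Week 9. As written, SAP 19.3.1 replaces a completed Week 9 questionnaire with an EOT questionnaire up to 27 days later in patients who stop on about Days 58-84, and the replaced value enters Tests 8 to 10. On the assumption of 50-80% completing 52 weeks at a constant stopping rate, this is at most about 2-6 of 140 patients. The shift in arm means is small and of unknown direction, and it can differ by arm because it depends on discontinuation.

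Outside the gatekept tests, the same rule can move Week 28 HRQoL and ECOG values by up to 83 days, and Week 28 hepcidin, iron, chemistry and lipid values by up to 34 days. Hepcidin, iron and lipids are exploratory endpoints analysed at Week 28 (SAP 12.3.4.6 and 12.3.4.7), with nominal p-values only.

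A reader might infer that the main efficacy result is at risk. It is not: transfusion independence is derived from transfusion dates and does not use these windows. Patients who complete 52 weeks are also unaffected, because their EOT visit falls in the Week 52 window.

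**What to change.** For post-baseline windows only, replace the last-assessment sentence in SAP 19.3.1 with:

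> *If more than one assessment falls in a window, the scheduled-visit assessment closest to the scheduled day is used; an early-termination EOT assessment is used only if no scheduled-visit assessment exists in that window.*

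Three additions are needed:

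1. Leave baseline as the last pre-dose value, as SAP 5.5 defines it.
2. State that displaced EOT values are listed and summarised as a separate EOT time point.
3. State whether displaced EOT values feed the LOCF sensitivity analysis in 19.8.2.

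The core change is one SAP sentence and one sort rule in the programs, with no new data. The small downside is that a displaced EOT score leaves the by-visit analysis, which is why it should be reported separately.

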### Appendix D - Dose Adjustment Rules for Patients who have TI for $\geq 56$ Days (8 weeks) – Maintenance Phase

A modified dose adjustment algorithm will apply to patients who have attained TI  $\geq 56$  days. The down titration of the dose is allowed at any time.

Change in Hb from 4 weeks earlier (g/dL)	Hemoglobin (Hb) Values			
	Hb <10.5 g/dL	Hb 10.5 to 12.9 g/dL	Hb >13.0 g/dL	Hb $\geq 13.5$ g/dL
< -1.0 * (or had RBC transfusion within 4 weeks)	↑	↑	No change	Hold, then resume dosing when: Hb <12 g/dL, at a dose that is reduced by one-dose level  Patients are to return weekly to monitor Hb until dosing can be resumed
-1.0 to 1.0	↑	No change	↓	
> 1.0	No change**	↓	↓	

\* A change in Hb from 4 weeks earlier of < -1.0 g/dL means a Hb value that is lower by more than 1.0 g/dL compared to 4 weeks earlier, e.g., a Hb of 9.4 g/dL compared to 10.6 g/dL 4 weeks earlier

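### SAP Table 7.6 closes the CBC windows at both ends, so 18 days belong to two visits and no rule says which visit takes a value drawn on one of them

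*SAP*

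**What the plan says.** SAP Section 19.3.1 assigns each assessment to an analysis visit by the treatment day on which it was taken. Table 7.6 does this for CBC in patients enrolled before Amendment 3 took effect. Its rows are:

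- Week 2: "Day 1 Post-Dose, Scheduled Day +3"
- Weeks 3 and 4: "Scheduled Day -3, Scheduled Day +3"
- Week 5: "Scheduled Day -3, Scheduled Day +7"
- odd weeks 7 to 27, and Week 28: "Scheduled Day -7, Scheduled Day +7"
- Week 31: "Scheduled Day -7, Scheduled Day +14"
- Weeks 35, 39 and 43: "Scheduled Day -14, Scheduled Day +14"
- Week 47: "Scheduled Day -14, Scheduled Day +21"
- Week 52: from 21 days before the scheduled day up to the Week 4 follow-up.

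All of these rows except Week 52 are printed with a square bracket at each end, so both end days are included. Week 52 has a round bracket at its upper end. Tables 7.1 to 7.5, 7.7 and 7.8 print a round bracket at the upper end throughout, so the upper day is excluded. Table 7.1 uses the same offsets as Table 7.6 from Week 7 on and differs there only in the bracket.

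The text above the tables says that when several assessments fall in one window, the last is used. It does not cover one assessment that falls in two windows.

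**The concern.** A windowing table should place each day in exactly one visit. Inclusive ends suit the three-day windows of Weeks 2 to 4, because those windows stop one day short of each other. Once the offsets widen to 7, 14 and 21 days, adjacent windows meet on the same day, and inclusive ends make them share it. A programmer following the table literally would assign a shared-day CBC to both visits. Another programmer might choose one visit, and two such choices need not agree.

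The outputs at stake are the by-visit CBC summaries (SAP Section 14.3), haemoglobin and its change from baseline at each scheduled visit and the mean haemoglobin plots to Weeks 28 and 52 (Section 12.3.4.4), and the two mean haemoglobin figures planned for the Week 28 analysis (Section 19.9).

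**Working it through.** **Scheduled days.** Table 7.6 gives 7 × (week − 1) + 1, except for Weeks 28 and 52, where it gives 7 × week + 1. So Week 5 = 29, Week 7 = 43, Week 9 = 57, Week 11 = 71, Week 27 = 183, Week 28 = 197, Week 31 = 211, Week 35 = 239, Week 39 = 267, Week 43 = 295, Week 47 = 323 and Week 52 = 365.

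**Check against the SAP's own figures.** The table footnotes place Week 28 two weeks after Week 27 and Week 52 six weeks after Week 47. The formulas give 197 − 183 = 14 days and 365 − 323 = 42 days, so both agree.

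**Windows as printed, both ends included.**

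| Visit | Days |
|---|---|
| Week 2 | 1 (post-dose) to 11 |
| Week 3 | 12 to 18 |
| Week 4 | 19 to 25 |
| Week 5 | 26 to 36 |
| Week 7 | 36 to 50 |
| Week 9 | 50 to 64 |
| Week 11 | 64 to 78 |
| … every 14 days … | |
| Week 27 | 176 to 190 |
| Week 28 | 190 to 204 |
| Week 31 | 204 to 225 |
| Week 35 | 225 to 253 |
| Week 39 | 253 to 281 |
| Week 43 | 281 to 309 |
| Week 47 | 309 to 344 |
| Week 52 | 344 onward |

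**Count.** There are 11 shared days at the boundaries from Weeks 5/7 to Weeks 25/27: 36, 50, 64, 78, 92, 106, 120, 134, 148, 162 and 176. There are 7 more from Weeks 27/28 to Weeks 47/52: 190, 204, 225, 253, 281, 309 and 344. That makes 11 + 7 = 18. Weeks 2 to 5 share no day with one another, and no day is left without a window.

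**Distance from schedule.** Days 36 to 204 in the list lie 7 days from the nearest scheduled day, Days 225 to 309 lie 14 days away, and Day 344 lies 21 days away. Protocol Section 6.5 allows ±1 day for Weeks 1 to 5 and ±2 days for Weeks 7 to 52, so a visit within tolerance never reaches a shared day.

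**What the last-value rule does with a CBC on Day 64.**

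| CBCs available | Week 9, as printed | Week 11, as printed | Week 9, upper end excluded | Week 11, upper end excluded |
|---|---|---|---|---|
| Days 57, 64, 71 | 64 | 71 | 57 | 71 |
| Days 64, 71 (none on 57) | 64 | 71 | none | 71 |
| Days 57, 64, then stopped | 64 | 64 | 57 | 64 |
| Day 64 only, then stopped | 64 | 64 | none | 64 |

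In every row the bracket changes Week 9, the earlier visit: either its value, or whether the patient counts there at all. Double use occurs only in the last two rows, where no later CBC falls in the Week 11 window. Week 11 is the same under both readings.

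**Check of the remedy.** Excluding the upper end from Week 5 to Week 47 and keeping Weeks 2 to 4 inclusive gives 0 shared days and 0 gaps. Excluding it on every row also gives 0 shared days but leaves Days 11, 18 and 25 in no window.

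**The case against.** The best reply is that this is a bracket slip with almost no reach, and much of that reply stands. Scheduled visits within tolerance never touch a shared day. The primary endpoint uses transfusion records (SAP Section 12.3.1). The haemoglobin responder endpoint uses moving 56-day windows (Section 12.3.4.4), not Table 7.6. Section 14.3 already keeps unscheduled values out of post-baseline laboratory safety summaries. Section 12.3.4.4 does not repeat that exclusion for the haemoglobin summaries, however, and an early end-of-treatment visit is a planned visit that can fall on any day. Some route to a shared-day value therefore remains.

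A reader might also infer more than the documents support:

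- **That n is inflated at the later visit.** It is not. Day 64 belongs to Week 11 with or without the bracket change, and Table 7.1 puts it there too. A stopped patient appears at Week 11 because of the windowing scheme itself.
- **That every shared-day value is analysed twice.** Double use also needs the next window to contain no later CBC.
- **That dose-hold monitoring makes this common.** Protocol Appendix D says "Patients are to return weekly to monitor Hb until dosing can be resumed", and such checks could fall 7 days after a scheduled visit. But checks on Days 57, 64, 71 and 78 give Week 9 = Day 64 and Week 11 = Day 78. That is displacement, with no value used for both Week 9 and Week 11. The rule also applies only after at least 56 days of transfusion independence, so it cannot produce a CBC on Day 36 or Day 50.
- **That separate windows by enrolment date are a flaw.** The difference is declared in the table's title, and Table 7.6 has Week 2 and Week 4 visits that Table 7.1 lacks.
- **That 1 shared day in every 14 gives a rate of affected values.** The documents give no distribution of off-schedule timing, and falling on a shared day is not enough for double use.

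**Conclusion.** Table 7.6 is wrong as written: 18 days belong to two visits and no rule resolves the tie. A CBC on such a day becomes the earlier visit's value, displacing an on-time value or adding to n at that visit if it had none. It also serves the later visit when nothing later falls in that window, the clearest case being an early end-of-treatment CBC.

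The effect is small, confined to off-schedule values in by-visit CBC and haemoglobin summaries and the mean haemoglobin plots. The number of affected values cannot be estimated, because the documents do not say how many patients enrolled before Amendment 3 or how often CBCs fell off schedule.

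The conclusion rests on reading square brackets as inclusive and round brackets as exclusive, which is the ordinary convention. That every other window table, and Table 7.6's own Week 52 row, excludes the upper end suggests a slip and not a choice.

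**What to change.** In Table 7.6, keep the inclusive upper end `]` for Weeks 2 to 4 and change it to the exclusive `)` for Weeks 5, 7 to 27, 28, 31, 35, 39, 43 and 47. Leave Week 52 as it is. Each day then belongs to exactly one visit. Do not apply the exclusive end to Weeks 2 to 4, because that would leave three days unassigned.

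The cost is a bracket edit in one table and the matching line of the windowing program. No endpoint definition, test or sample size changes.
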